3.2.5 Safety Variables

3.2.5.1 Adverse event

An AE is any untoward medical occurrence in a participant or clinical study participant, temporally associated with the use of a study treatment, whether or not considered related to the medicinal product.

AEs will be collected from the signing of the informed consent form (ICF) to the follow-up visit (Visit 5/End of study). Each AE verbatim term will be coded to a system organ class and a preferred term using the latest version of Medical Dictionary for Regulatory Activities (MedDRA).

For patient level summaries, if more than one AE is coded to the same PT for the same patient, the patient will be counted only once in summary tables using the most serious grading on causal relationship to study treatment.

3.2.5.2 Serious Adverse Event (SAE)

An SAE is an AE occurring during any study phase (i.e., run-in, treatment, washout, follow-up), that fulfills one or more of the following criteria:

- Results in death
- Is life-threatening
- Requires inpatient hospitalization or prolongation of existing hospitalization
- Results in persistent disability or incapacity
- Is a congenital abnormality or birth defect
- Is an important medical event that may jeopardize the subject or may require medical intervention to prevent one of the outcomes listed above

3.2.5.3 Suspected Unexpected Serious Adverse Reactions (SUSARs)

SUSAR is defined as an AE that is serious, associated with the use of the study treatment, and unexpected and has additional reporting requirements, as described in section 10.3 of the Clinical Study Protocol (CSP).

3.2.5.4 Clinical laboratory testing

Laboratory data will be collected throughout the study, from screening to the follow-up visit as per the study plan described in the CSP. Hematology, serum chemistry, urinalysis, and others as clinically indicated will be collected as described in section 10.2 of the CSP.

Missing laboratory data will not be imputed. However, laboratory assessment values of the form of " $<x$ " (i.e., below the lower limit of quantification) or " $>x$ " (i.e., above the upper limit of quantification) will be imputed as " x " in the calculation of summary statistics but displayed as " $<x$ " or " $>x$ " in the listings.

3.2.5.5 Cocaine Selective Severity Assessment (CSSA)

A modified version of the CSSA will be used to measure potential withdrawal signs and symptoms from the study treatment; "cocaine" will be replaced with "study drug". The CSSA includes psychiatric symptoms of general safety interest such as changes in sleep, anxiety, energy level, activity level, tension, attention, paranoid ideation, anhedonia, depression, suicidality, and irritability. Items are rated on a scale of 0-7, and a total score is derived by summing the individual items.

3.2.5.6 Prospective Suicidality Assessment

The CSSA item 17, "suicidality", will be used to monitor participants for suicidality during the study (whether or not abuse-related). A score of ≥ 3 will be considered an AE.

3.2.5.7 Pregnancy records

Details of all pregnancies in female participants and female partners of male participants after the start of study treatment and until at least 5 terminal half-lives after the last dose will be collected. Abnormal pregnancy outcomes (e.g., spontaneous abortion, fetal death, stillbirth, congenital anomalies, ectopic pregnancy) are considered to be SAEs.

4 STATISTICAL METHODS

4.1 Data Quality Assurance

All tables, figures and data listings to be included in the report will be independently checked for consistency, integrity and in accordance with standard PAREXEL procedures. The data extraction will be set to appropriate date so that all data cleaning activities at site are taken care of.

4.2 Study Subjects

4.2.1 Disposition of Subjects

A clear accounting of the disposition of all enrolled subjects who enter the study will be provided, from screening to study completion.

Screen failures are defined as subjects who consent to participate in the clinical study but are not subsequently randomized to study treatment/entered into the study. Summaries of subject disposition will be presented by treatment and overall.

The following patient disposition summaries will be provided

- A summary of the number and percentage of subjects who were screened, screen failure, randomized, randomized but were not treated (not a single dose of the study treatment) will be provided. This summary will be based on total screened subjects.
- A separate summary table for subjects who completed, discontinued and the primary reason(s) for discontinuation will be provided for each treatment group. This summary will be based on mITT Population.
- Subject disposition including the subject status (completer, Yes/No), demographic data (age and race), screening date, study product start date and time, the duration in the study or trial, date of discontinuation and the specific reason for discontinuation, will be listed for randomized subjects by product group and center.

4.2.2 Protocol Deviations

Protocol deviations will be tracked by the study team throughout the conduct of the study. Data will be reviewed prior to un-blinding and closure of the database to ensure all important deviations are captured and categorized. Subjects with major protocol deviations (defined below) will be excluded from the PP population.

Major protocol deviations are defined as those deviations from the protocol that are likely to have an impact on the subject's rights, safety, well-being, and/or on the validity of the data for primary analysis. This will include all those deviations to be reported in the clinical study report (CSR).

The impact of major protocol deviations on the efficacy and/or safety results will be investigated by assessing the robustness of the study results and conclusions to the choice of analysis population (see [Section 4.4](#)), both including and excluding data potentially affected by major protocol deviations. The final determination of major protocol deviations and the exclusion of patients from each of the analysis populations will be made prior to database lock. Please refer to the study protocol deviation specification for more information.

In the event that a subject is allocated the incorrect study treatment as per the study randomization list, it will be considered as a protocol deviation.

The number of subjects with protocol deviations will be summarized by category (Major or Minor) and deviation classification overall and by treatment group. Protocol deviations will be listed with date and study day of occurrence, deviation category, deviation description and analysis populations from which subject is excluded.

The number of subjects included in each analysis population will be summarized. A listing of subjects included in each analysis population will also be provided. Subject exclusion from analysis sets will be listed with reasons for exclusions.

Blinding of the study will be maintained as per the Blinding Maintenance Plan which has been developed and approved on 13March2019.

4.3 Analysis Sets

Enrolled Population

All participants who signed the ICF (including screening failures).

Modified Intent to Treat (mITT) Population

The efficacy summaries and analyses will be based on the mITT Population, which is based upon the Intention-to-Treat principle. The mITT Population comprises all participants who are randomized, take at least 1 dose of any of the study treatments, and have at least 1 measurement on the primary endpoint. The mITT population will therefore include patients who have a primary endpoint measurement at either Visit 2 (baseline) or Visit 4 (on treatment), or both. Participants will be analyzed for efficacy according to the treatment group into which they are randomized.

If a subject is allocated the incorrect study treatment as per the study randomization list, subjects will be summarized and analyzed 'as randomized' i.e. by randomized treatment group.

Safety Population

The safety summaries and analyses will be based on the Safety Population. The Safety Population consists of all participants who are randomized and receive at least 1 dose of any of the study treatments. Participants will be analyzed "as actually received" (i.e., according to the actual treatment received during randomization).

Per Protocol (PP) Population

The PP Population consists of all participants without any major protocol violations that could influence efficacy assessment, and who are at least 80% compliant with the study medication. Participants in this population will be analyzed according to the treatment they actually received.

Upon database release, protocol deviation and analysis set outputs will be produced and will be sent to Apnimed for review. An analysis population classification meeting will be arranged to discuss the outputs and to decide which subjects and/or subject data will be excluded from certain analyses. Decisions made regarding the exclusion of subjects and/or subject data from analyses will be made prior to unblinding and will be documented and approved by Apnimed.

Sensitivity analyses will be performed on the PP population for key primary and key secondary efficacy endpoints (key comparisons for which sequential order is specified, please refer section 9.4 of the protocol or [4.9.1.4](#) of the SAP) to understand the impact of

major protocol deviations on study results. Sensitivity analyses will separately be performed on the PP population excluding patients whose randomization was “forced”.

4.4 Demographics and Baseline Characteristics

Descriptive statistics (number of subjects [n], mean, median, standard deviation [SD], minimum and maximum) for the continuous variables and frequency (n) and percentages (%) for categorical variables will be provided for demographic variables.

The continuous variable includes age (years) height (Meter), weight (kg), BMI, International Prostate Symptom Score (IPSS), AHI Score and categorical variables include gender, race, and Ethnicity, STOP BANG Score (5-8 [High risk of OSA], 3-4 [Intermediate OSA], 0-2[Low Risk]).

Age will be calculated as the number of complete years between a subject's birth date and the date of informed consent. If age is missing but date of birth is present, age will be calculated as follows (without rounding):

Age (years) = (study day 1 – date of birth) / 365.25

This will be determined from the date of birth (birth date in the Demographics eCRF page) and baseline visit ('visit 1' in the Date of visit eCRF page). If the day of birth is missing, the first day of the month will be imputed and if day and month are missing January 1st will be imputed.

4.5 General Presentation Considerations

All statistical analyses will be performed using SAS® software Version 9.3 or later.

Medical history and AEs will be coded using the latest version of MedDRA. The frequency count and percentage of subjects will be summarized according to the coded terms of system organ class (SOC) and preferred term (PT). Subject-wise data listing will be provided.

For participants who are eligible and enroll in the study, the screening PSG night will serve as the baseline measure for AHI and other PSG efficacy and safety endpoints. Baseline measures for additional secondary and tertiary endpoints based on home oximetry will be recorded at home during the placebo period, and these endpoint measures will continue to be collected over the subsequent at-home study treatment dosing period. On the final night of dosing (Visit 4), participants will return for inpatient PSG.

A participant is considered to have completed the study if he/she has completed all phases including Screening (visit 1), Baseline (visit 2), placebo baseline (2 night (Day 1-2), low dose run-in or placebo night (3 night [Day 3-5 +2]), ATO/OXY (mg) or placebo 7 night (Day 6-12 +/- 2) and the final Follow-up visit or the last scheduled procedure shown in the Schedule of Activities (SoA) (Appendix).

The end of the study is defined as the date of the last visit of the last participant in the study or last scheduled procedure shown in the SoA for the last participant in the study globally.

Continuous data will be summarized in terms of the mean, standard deviation (SD), median, minimum, maximum and number of observations, unless otherwise stated.

Continuous data that are expected to be skewed will be presented in terms of the maximum, upper quartile, median, lower quartile, minimum and number of observations. The minimum and maximum will be reported to the same number of decimal places as the raw data recorded in the database. The mean, median, lower quartile and upper quartile will be reported to one more decimal place than the raw data recorded in the database. The SD will be reported to two more decimal places than the raw data recorded in the database. In general, the maximum number of decimal places reported shall be four for any summary statistic.

4.6 Medical History and Concomitant Therapy

Relevant medical history (past and current) and relevant surgical history will be coded using the latest version of MedDRA.

Concomitant procedures will be coded using the latest version of MedDRA, and will be summarized for the safety population by SOC and PT.

Moreover, the prohibited or restricted concomitant therapies (see section 6.5 of the CSP) will be summarized.

4.7 Prior and Concomitant Medications

The World Health Organization (WHO) Drug dictionary will be used for concomitant medication coding.

Medication start and stop dates will be compared to the date of first dose of study medication to allow medications to be classified as either Prior only, both Prior and Concomitant, or Concomitant only. Medications starting after the completion/withdrawal date will be listed but will not be classified or summarized.

Medications that start and stop prior to the date of first dose of study medication will be classified as Prior only. If a medication starts before the date of first dose of study medication and stops on or after the date of first dose of study medication, then the medication will be classified as both Prior and Concomitant. Medications will be classified as Concomitant only if they have a start date on or after the date of first dose of study medication.

If medication start and/or stop dates are missing or partial, the dates will be compared as far as possible with the date of first dose of study medication. Medications will be assumed to be Concomitant only, unless there is clear evidence (through comparison of partial dates) to suggest that the medication started prior to the first dose of study medication. If there is clear evidence to suggest that the medication started prior to the first dose of study medication, the medication will be assumed to be both Prior and Concomitant, unless there is clear evidence to suggest that the medication stopped prior to the first dose of study medication. If there is clear evidence to suggest that the medication stopped prior to the first dose of study medication, the medication will be assumed to be Prior only.

4.8 Treatment Exposure / Compliance

4.8.1 Treatment Exposure

Exposure to study treatment will be summarized by treatment group for the safety population by durations of drug exposure (days), total number of capsules received, and total number of capsules dispensed. Doses that were not given because the patient discontinued will not be summarized.

4.8.2 Compliance

Treatment compliance is calculated as the proportion in percentage of the scheduled expected number of doses, i.e. (Actual exposure/Expected exposure) *100.

A table with proportion of subjects with compliance and Non-compliance (Subject would be considered non-compliant if the subject consumes less than 80% of the total amount of recommended dose.) will be presented. Non-compliance will be assessed on a subject by subject basis. Those subjects with treatment compliance less than 80% will be excluded from the PP analysis. Any subject excluded from PP analysis will be clearly documented. Treatment compliance listing will be presented

4.9 Efficacy Evaluation

4.9.1 Analysis and Data Conventions

The high-dose AD036 in this study is atomoxetine 75 mg/ oxybutynin 5 mg, similar to the dose used in initial human studies (atomoxetine 80 mg/oxybutynin 5 mg). To explore the potential efficacy and safety of lower atomoxetine and oxybutynin doses, the following 2 additional dose arms will be studied: atomoxetine 75 mg/oxybutynin 1.5 mg and atomoxetine 25 mg/oxybutynin 5 mg. This Phase 2 clinical study will further examine the efficacy and safety of lower dose AD036 versus placebo.

The primary objective (s) of this study is to assess the efficacy of 3 different fixed doses of AD036 (the combination of atomoxetine and oxybutynin) vs. placebo.

The primary endpoint is the proportion of participants with $\geq 50\%$ reduction in AHI from baseline to the second PSG visit (Visit 4).

The primary comparison of the study is

- ATO 75 mg/OXY 5 mg vs placebo in the proportion of participants with $\geq 50\%$ reduction in AHI from baseline to the second PSG visit (Visit 4).

Primary null hypothesis will be

H_0 : Odds ratio for ATO 75 mg/OXY 5 mg versus placebo in participants with $\geq 50\%$ reduction in AHI from baseline to the second PSG visit (Visit 4) = 1

Primary alternative hypothesis will be

H_1 : Odds ratio for ATO 75 mg/OXY 5 mg versus placebo in participants with $\geq 50\%$ reduction in AHI from baseline to the second PSG visit (Visit 4) $\neq 1$.

The other efficacy comparisons of interest also will be tested using logistic regression similar to primary efficacy hypothesis.

Participants that discontinue prior to the second PSG visit will not be replaced and will be considered non-responders.

When change from baseline is assessed at a post-baseline visit, unless otherwise specified, only patients with both baseline and post-baseline measurements will be included in the analyses. If baseline or post-baseline value is missing for a patient, then the change from baseline will be set to missing.

For all PSG safety and efficacy endpoints the screening PSG night (Visit 2) will serve as the baseline. For additional secondary and tertiary endpoints based on home oximetry, the average of the two baseline nights (Placebo baseline two night) will serve as the baseline.

Unless otherwise stated, if baseline data is missing no derivation will be performed and will be set to missing.

For all efficacy endpoints, descriptive summary statistics for absolute values, change or percent change from baseline, if applicable, will be provided by analysis visits for mITT population and PP population.

For primary and key secondary endpoint analysis based on logistic regression odds ratio and 95% Wald confidence limits will be presented.

For primary and all key secondary endpoint line graph or bar graph will be created and details will be provided in the TLFs shell document.

4.9.1.1 Multi-center Studies

For the summaries and analyses purpose, the term ‘Center’ will be used to define each investigator site.

4.9.1.2 Adjustments for Covariates

Baseline values for all endpoint will be included as a covariate for all efficacy analysis.

4.9.1.3 Handling of Dropouts or Missing Data

Participants that discontinue prior to the second PSG visit will not be replaced and will be considered non-responders (<50% improvement in the AHI score).

Subject with missing baseline data will also be consider as the non-responder.

Responder are defined as the participant who shows $\geq 50\%$ improvement in the AHI Score.

For all other endpoint missing data will not be imputed.

4.9.1.4 Multiple Comparisons/Multiplicity

Hypothesis tests will be performed in a sequential manner to avoid the need to adjust type I error rates for multiplicity, at a 2-sided 0.05 significance level. The sequential order of hypothesis tests will occur as follows:

- Comparison of the proportion of participants with $\geq 50\%$ improvement in AHI from baseline to the second PSG visit in the 75/5 dose group compared with placebo.
- Percent change AHI, high-dose arm vs. placebo.
- Proportion of participants with $\geq 50\%$ improvement in AHI, measured in the supine sleeping position, from baseline to the second PSG visit in the 75/5 dose group compared with placebo.
- Proportion of participants with $\geq 50\%$ improvement in Oxygen desaturation index from baseline (average of 2 baseline nights) to study treatment nights (average of 6 nights) for the 75/5 dose group compared with placebo.
- Change from baseline in the Epworth Sleepiness Scale (ESS) from baseline to the second PSG visit in the 75/5 dose group compared with placebo.
- Change from baseline in the Participant Global Impression of Severity (PGI-S) from baseline to the second PSG visit in the 75/5 dose group compared with placebo.

- Proportion of participants with $\geq 50\%$ improvement in AHI from baseline to the second PSG visit in the 75/5 dose group compared with the lower treatment dose of 25/5.
- In the case that a statistically significant result for the AHI comparison of dose 75/5 to 25/5 is observed, then the proportion of participants with $\geq 50\%$ improvement in AHI from baseline to the second PSG visit in the 75/5 dose group will be compared with the lower treatment dose of 75/1.5.

4.9.1.5 Interim Analyses

No formal interim analysis is planned.

4.9.1.6 Examination of Subgroups

As a part of the additional exploratory analysis the uniformity of the treatment effect for the primary efficacy variable will be examined for the following subgroups:

1. Subgroup 1 – Baseline AHI Score ≤ 30 and BMI < 35 ,
2. Subgroup 2 - Baseline AHI Score > 30 or BMI ≥ 35

The homogeneity of the treatment effect across subgroups will be investigated. In addition, a statistical test for the presence of a treatment-by-subgroup interaction will be performed, by including the interaction term in the primary analysis model. The treatment-by-subgroup interaction will be investigated at 10% level ($p < 0.10$).

Summaries of the primary efficacy variable by treatment group and subgroup will be produced. No formal statistical analysis will be performed within subgroup.

4.9.2 Primary Efficacy Variable(s)

Primary efficacy variable is participants with $\geq 50\%$ improvement in AHI score from baseline.

Primary efficacy variable will be summarized by treatment group and visit.

Summaries will include the total number of subjects with assessments, the number of participants with missing measurements, proportion of subjects with $\geq 50\%$ improvement in AHI from baseline and associated 95% confidence intervals.

The primary efficacy endpoint will be analyzed using a logistic regression model with the treatment group as factor and baseline AHI score as a covariate. Estimate of the odds ratio along with associated 95% Wald confidence interval (CI) and two-sided p-value will be presented for primary comparison between 75 mg/5mg dose group and placebo.

Odds ratio estimates, CIs, and p-values will also be presented for other efficacy comparisons under the primary objective:

1. 75/1.5 dose arm vs Placebo arm
2. 25/5 dose arm vs Placebo arm
3. 75/5 dose arm vs. 75/1.5 dose arm

4. 75/5 dose arm vs. 25/5 dose arm
5. 75/1.5 dose arm vs 25/5 dose arm

In the situation of zero events (or < 5 participants) in treatment groups, the logistic model may fail to provide valid parameter estimates. In this situation exact logistic regression (Fisher's exact test) can be used to compare the proportions across treatment groups.

A by-subject listing of the primary efficacy data will be provided.

The primary endpoint analysis will be based on mITT and PP population.

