4.9.3 Secondary Efficacy Variables

To control the type I error, a sequential testing procedure will be employed with the order of hypothesis defined as in [Section 3.2.2](#) above. All comparisons will be carried out and their result will be interpreted carefully.

Percent change AHI, high-dose arm vs. placebo.

Percent change AHI will be compared between high-dose arm and placebo group using an analysis of covariance (ANCOVA) model with treatment group as factor and baseline AHI (Visit 2) as a covariate. In the ANCOVA model.

Adjusted means, Standard error (SE) of Adjusted means, 95% confidence intervals, within treatment p-values for each treatment group, treatment group difference, 95% confidence interval of the difference and the between-treatment p-values based on the statistical model described above will also be presented

Similar analysis will be carried out for the following treatment comparisons on the percent change AHI score at two-sided 0.05 level of significance.

1. 75/1.5 dose arm vs Placebo arm
2. 25/5 dose arm vs Placebo arm
3. 75/5 dose arm vs. 75/1.5 dose arm
4. 75/5 dose arm vs. 25/5 dose arm
5. 75/1.5 dose arm vs 25/5 dose arm

Proportion of participants with $\geq 50\%$ improvement in AHI, measured in the supine sleeping position, from baseline (Visit 2) to the second PSG visit (Visit 4) in the 75/5 dose group compared with placebo.

Proportion of patients with $\geq 50\%$ improvement in AHI, measured in the supine sleeping position, from baseline to the second PSG visit between 75/5 dose and placebo group will be analyzed using a logistic regression model with the treatment group as factors and baseline AHI Score as a covariate.

Estimate of the odds ratio along with associated 95% Wald confidence interval (CI) and two-sided p-value will be presented

Similar analysis will be carried out for the following treatment comparison on this efficacy variable at two-sided 0.05 level of significance.

1. 75/1.5 dose arm vs Placebo arm
2. 25/5 dose arm vs Placebo arm
3. 75/5 dose arm vs. 75/1.5 dose arm
4. 75/5 dose arm vs. 25/5 dose arm
5. 75/1.5 dose arm vs 25/5 dose arm

Proportion of participants with $\geq 50\%$ improvement in at-home Oxygen desaturation index from baseline (average of 2 baseline nights) to study treatment nights (average of 6 nights) for the 75/5 dose group compared with placebo.

The oxygen desaturation index is the average number of oxygen desaturations 4% or more below the baseline level per hour.

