Proportion of patients with $\geq 50\%$ improvement in Oxygen desaturation index from baseline to study treatment nights (average of 6 nights) between 75/5 dose and placebo group will be analyzed using a logistic regression model with the treatment group as factors and baseline Oxygen desaturation index as a covariate.

Estimate of the odds ratio along with associated 95% Wald confidence interval (CI) and two-sided p-value will be presented

Similar analysis will be carried out for the each of following treatment comparison on this efficacy variable

All statistical tests of hypotheses will be two-sided and will employ a level of significance of $\alpha = 0.05$.

1. 75/1.5 dose arm vs Placebo arm
2. 25/5 dose arm vs Placebo arm
3. 75/5 dose arm vs. 75/1.5 dose arm
4. 75/5 dose arm vs. 25/5 dose arm
5. 75/1.5 dose arm vs 25/5 dose arm

Change in the ESS from baseline to the second PSG visit in the 75/5 dose group compared with placebo.

Change from baseline in the ESS at second PSG visit (visit 4) will be compared between 75/5 dose and placebo group using ANCOVA with treatment group as factor and baseline results as a covariate.

Adjusted means, Standard error (SE) of Adjusted means, 95% confidence intervals, within treatment p-values for each treatment group, treatment group difference, 95% confidence interval of the difference and the between-treatment p-values based on the statistical model described above will also be presented

Similar analysis will be carried out for the each of following treatment comparison on this efficacy variable.

All statistical tests of hypotheses will be two-sided and will employ a level of significance of $\alpha = 0.05$.

1. 75/1.5 dose arm vs Placebo arm
2. 25/5 dose arm vs Placebo arm
3. 75/5 dose arm vs. 75/1.5 dose arm
4. 75/5 dose arm vs. 25/5 dose arm
5. 75/1.5 dose arm vs 25/5 dose arm

Change in the PGI-S from baseline to the second PSG visit in the 75/5 dose group compared with placebo.

Change from baseline in the PGI-S at second PSG visit (visit 4) will be compared between 75/5 dose and placebo group using ANCOVA with treatment group as factor and baseline results as a covariate.

Adjusted means, Standard error (SE) of Adjusted means, 95% confidence intervals, within treatment p-values for each treatment group, treatment group difference, 95% confidence interval of the difference and the between-treatment p-values based on the statistical model described above will also be presented

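### The sparse-data fallback for the primary responder test (SAP 4.9.2) is optional, has two undefined triggers and treats two different tests as one; it should be one binding rule

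*SAP*

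**What the plan says.** SAP 4.9.2 gives the default clearly: a logistic model with treatment as factor and baseline AHI as covariate. "Estimate of the odds ratio along with associated 95% Wald confidence interval (CI) and two-sided p-value will be presented for primary comparison".

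The same section then adds a fallback. "In the situation of zero events (or < 5 participants) in treatment groups, the logistic model may fail to provide valid parameter estimates". The next sentence offers exact logistic regression, with a bracketed gloss naming Fisher's "exact test) can be used to compare the proportions across treatment groups".

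SAP 4.9.1.2 sets a general rule with no stated exception: "Baseline values for all endpoint will be included as a covariate for all efficacy analysis".

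Two secondary endpoints in the testing sequence are also binary, and SAP 4.9.3 gives each a logistic model. Supine AHI response "between 75/5 dose and placebo group will be analyzed using a logistic regression model with the treatment group as factors and baseline AHI Score" as covariate. Oxygen desaturation index (ODI) response is analysed "using a logistic regression model with the treatment group as factors and baseline Oxygen desaturation index as a covariate". Neither paragraph repeats the fallback. SAP 4.9.1 says only: "The other efficacy comparisons of interest also will be tested using logistic regression similar to primary efficacy hypothesis".

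Protocol 9.4 gives the order of testing but names no test.

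**The concern.** The fallback leaves three things open.

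- **Whether to switch.** The wording permits a change of test but does not require it.
- **When to switch.** There are two triggers, zero events or fewer than five participants. The second does not say whether it counts responders, or whether one compared arm or both must meet it.
- **What to switch to.** Exact logistic regression and Fisher's exact test coincide only when treatment is the sole term. An exact conditional model that keeps baseline AHI is a different analysis. Fisher's test drops the covariate that SAP 4.9.1.2 asks for.

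The test that yields the primary p-value could therefore be settled after the arm counts are known. This matters because SAP 4.12 expects few placebo responders, and because the primary test opens the sequence in SAP 4.9.1.4: "Hypothesis tests will be performed in a sequential manner to avoid the need to adjust type I error rates for multiplicity". Zero of 35 on placebo is the best placebo outcome for the drug, yet it leaves the planned Wald test without a finite odds ratio.

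**Working it through.** **Inputs (SAP 4.12).** 35 per arm; two-sided alpha 0.05; stated power 90%; responder rates 37% vs 5%, or 46% vs 10%. Expected placebo responders: 35 × 0.05 = 1.75, or 35 × 0.10 = 3.5. Dropouts count as non-responders, so the denominator is taken as 35.

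**Method.** All 36 × 36 pairs of responder counts are enumerated, weighted by their binomial probabilities, without the covariate.

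**The plan's own figure.** Fisher's exact test gives 90.7% and 90.6%, so the stated 90% reproduces. At 36% and 45% on the high dose, Fisher's power is 89.0% in both cases. So 37% and 46% are the lowest whole-percent rates that reach 90% under that test. The pooled normal formula gives 92.5% and 93.6%.

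**How often each trigger is met on placebo.**

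- Zero responders: 0.95^35 = 16.6%; 0.90^35 = 2.5%.
- Fewer than five responders, if that is what is meant: Σ(k=0..4) C(35,k) p^k (1−p)^(35−k) = 97.1% at 5% and 73.1% at 10%.

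**Unadjusted Wald test.** With a responders on high dose and b on placebo:

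z = ln[a(35−b) / (b(35−a))] / √(1/a + 1/b + 1/(35−a) + 1/(35−b))

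This is not estimable when b = 0; such tables are counted as no rejection. Fisher's test at 6 vs 0 gives p = 0.025.

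| Rule | Power, 37% vs 5% | Power, 46% vs 10% |
|---|---|---|
| Wald, switch never made | 76.6% | 91.6% |
| Fisher at zero responders in either arm, otherwise Wald | 93.2% | 94.1% |
| Fisher below five responders in either arm, otherwise Wald | 91.1% | 93.1% |
| Fisher always | 90.7% | 90.6% |
| Firth, penalised likelihood-ratio test, always | about 94.6% | about 94.1% |

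Rows 1 and 2 differ by 93.2 − 76.6 = 16.6 points at 37% vs 5%. This is essentially the probability of a placebo arm without responders.

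**Where the two triggers disagree.** With drug ahead of placebo, only two estimable tables change significance:

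- 10 vs 3: ln(320/75) = 1.451, SE = √(0.1000 + 0.3333 + 0.0400 + 0.0313) = 0.710, z = 2.04, Wald p = 0.041; Fisher p = 0.062.
- 11 vs 4: ln(341/96) = 1.268, SE = √(0.0909 + 0.2500 + 0.0417 + 0.0323) = 0.644, z = 1.97, Wald p = 0.049; Fisher p = 0.078.

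Their joint probability is 0.0135 + 0.0076 = 2.1% at 37% vs 5%, and 0.0036 + 0.0061 = 1.0% at 46% vs 10%. It falls to 0.17% at 50% vs 5% and below 0.01% at 60% vs 5%.

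**Type I error.** Over common responder rates up to 40%, taking whichever of the two trigger rules gives the smaller p-value yields at most 4.8%. Firth also reaches at most 4.8%.

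**Check with the covariate.** A simulation used an assumed skewed baseline AHI, a log-odds slope of 0 or −0.7 per SD, and 4,000 runs per setting. Wald power without the switch was 76.1% to 78.6% at 37% vs 5%, and 90.4% to 91.9% at 46% vs 10%. Across both scenarios it was 93.1% to 94.4% with the zero-event switch and 91.2% to 93.6% with the below-five switch. Firth was not simulated with the covariate.

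**The case against.** The default model is fixed, and only a fallback branch is loose. A competent analyst facing 0 of 35 would see that the model had failed and would use the exact method that the SAP offers. Once that is done, power is at least 91% under either trigger and the error rate is controlled. The disagreement is confined to effects near the design's floor, whereas SAP 4.12 cites 8 of 9 responders in earlier data. SAP 4.9.2 can also be read as a specific exception to the general covariate rule. All of this limits the size of the point. It does not remove it: the primary p-value should follow from a rule, not from an expectation of good judgement after the counts are seen.

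Several stronger readings are tempting, and the documents do not support them.

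- **That the fallback applies in most trials.** The 97.1% and 73.1% hold only if the second trigger means responders in either arm. If both compared arms must have fewer than five, the probability is 0.07% or 0.001%. If it means enrolled participants, it is irrelevant at 35 per arm.
- **That the looseness inflates type I error.** The enumeration shows that it does not.
- **That the later responder tests would break the sequence.** No placebo rate is given for supine AHI or ODI response. If it were 5%, 10% or 15%, zero of 35 would have probability 16.6%, 2.5% or 0.3%. The SAP 4.9.1 wording that these tests are run like the primary may already carry the fallback over.
- **That SAP 4.12 is wrong because it names no test.** Its 90% reproduces under Fisher's exact test.

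**Conclusion.** The point holds as a defect in the fallback rule, of minor to should-fix severity. It goes beyond missing detail: at the SAP's own 5% placebo rate, the named Wald test is unusable in about one trial in six, and the text permits the alternative without requiring it. The worst case, in which the switch is never made, costs about 17 points of power at 37% vs 5% and about 2.5 points at 46% vs 10% (94.1 − 91.6). If the switch is made, which trigger applies alters significance in 2.1% or 1.0% of trials.

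The exact figures assume 35 analysed per arm, the SAP 4.12 rates, no covariate, and zero-responder tables counted as non-significant under Wald. The covariate simulation gives similar values under its assumed baseline distribution.

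**What to change.** Replace the permissive sentence in SAP 4.9.2 with one binding rule.

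- **Preferred.** Use Firth-penalised logistic regression with treatment and baseline AHI at all counts, with a penalised likelihood-ratio p-value. It keeps the covariate and needs no trigger. Unadjusted, its power at least matches either switching rule, and its type I error is at most 4.8% for common rates up to 40%. The drawback is a less familiar method.
- **Acceptable minimum.** Make the switch mandatory, define one trigger as a count of responders in either compared arm, and name one method. If that method is Fisher's exact test, state the exception to SAP 4.9.1.2.

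State in SAP 4.9.3 that the same rule applies to the supine AHI and ODI responder tests. SAP 4.12 needs no change.

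The cost is a few sentences and a standard software option, with no new data and no more participants. The change should be made before unblinding.
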